13.4.5 Descriptive Analyses

Descriptive analyses will be reported separately by baseline severity group and study outcome group. Continuous baseline measures will be reported as 1) mean (or geometric mean) with standard deviation, or 2) median with 1st and 3rd quartile, as appropriate. Categorical baseline and demographic characteristics and participant disposition will be reported as frequencies and proportions.

13.5

13.6 Statistical Hypotheses

13.6.1 Hypotheses for the Primary Objective

The null and alternative hypotheses for the primary objectives will be assessed for children and adults separately and are as follows:

Test for differences in type 2-high status by baseline severity:

- H_0 : The percentage of participants with type 2-high status does not differ between severity groups.
- H_A : The percentage of participants with type 2-high status differs between severity groups.

Test for differences in type 2 overall gene expression by baseline severity:

- H_0 : Geometric mean of expression for the type 2 inflammation network genes does not differ between severity groups.
- H_A : Geometric mean of expression for the type 2 inflammation network genes differs between severity groups.

13.6.2 Hypotheses for Secondary Objective 1

The null and alternative hypotheses for the SOs will be assessed on a gene level, for each visit separately, and are as follows:

Test for differences in gene expression by current severity group (pairwise differences, stratified by skin type and age cohort):

- H_0 : Gene expression does not differ between severity groups.
- H_A : Gene expression differs between severity groups.

Test for whether differences between severity groups (pairwise) are differential by skin type (lesional/non-lesional):

- H_0 : Differences in gene expression between severity groups do not differ by skin type (lesional/non-lesional).
- H_A : Differences in gene expression between severity groups differ by skin type (lesional/non-lesional).

Test for whether differences between severity groups (pairwise) are differential by age cohort (children/adults):

- H_0 : Differences in gene expression between severity groups do not differ by age cohort (children/adults).
- H_A : Differences in gene expression between severity groups differ by age cohort (children/adults).

13.6.3 Hypotheses for Secondary Objective 2

The null and alternative hypotheses for the SOs will be assessed on a gene level and are as follows:

Test for changes in gene expression over time (stratified by outcome group, skin type, and age cohort):

- H_0 : Gene expression does not differ between Day 7 and end of study.
- H_A : Gene expression differs between Day 7 and end of study.

Test for whether changes in gene expression over time are differential by study outcome group:

- H_0 : Changes in gene expression between Day 7 and end of study do not differ between study outcome groups.
- H_A : Changes in gene expression between Day 7 and end of study differ between study outcome groups.

Test for whether changes in gene expression over time are differential by skin type (lesional/non-lesional):

- H_0 : Changes in gene expression between Day 7 and end of study do not differ by skin type (lesional/non-lesional).
- H_A : Changes in gene expression between Day 7 and end of study differ by skin type (lesional/non-lesional).

Test for whether changes in gene expression over time are differential by age cohort (children/adults):

- H_0 : Changes in gene expression between Day 7 and end of study do not differ by age cohort (children/adults).
- H_A : Changes in gene expression between Day 7 and end of study differ by age cohort (children/adults).

13.7 Sample Size Considerations

13.7.1 Statistical power for study analyses

The study will enroll 600 participants in total, including: 300 adults with AD, 100 non-AD adults, 150 children with AD, and 50 non-AD children. Of the 450 AD participants, approximately 390 will be dupilumab-naïve. Dupilumab-naïve participant enrollment will be targeted to achieve approximately two thirds moderate-to-severe participants (moderate-to-severe AD adults = 160, moderate-to-severe AD children = 80) and one third mild participants (mild AD adults = 100, mild AD children = 50). We will target approximately 60 long-term dupilumab participants who are currently being treated with dupilumab and have received dupilumab for ≥ 4 months (20 children, 40 adults). These long-term dupilumab participants will be excluded from the primary objective and secondary objective #1.

Based on these population targets, we make several additional assumptions regarding sizes for the study outcome groups. Among the dupilumab-naïve AD participants, only those who fail topical steroid treatment will initiate dupilumab treatment. Currently, we project a 50% failure rate for topical steroids among the dupilumab-naïve moderate-to-severe participants and a 5% failure for the dupilumab-naïve mild AD participants ([Brunner et al, 2016](#)). Therefore, we anticipate topical steroid non-response in 85 adult AD participants and 43 children with AD, who will go on to receive dupilumab. Finally, of these dupilumab-naïve participants who receive dupilumab

during the study, we expect that approximately 40% will achieve $EASI \leq 7$, per the following reference ([Beck et al, 2014](#)).

This sample size powers the primary comparison of type 2-high inflammation status by baseline severity group at 80%. Specific details about power and sample size for the primary and secondary objectives are below.

Power analysis for Primary Objective

The primary objective for the study is to determine if the type 2-high non-lesional skin (skin tape) endotype is associated with current mild versus moderate-to-severe AD disease.

[figure not shown]
Assuming a prevalence of 50% for type 2-high status, as well as the group-level sample sizes in Table 13.7.1.1, we have 80% power to detect statistical significance for the odds ratios listed in the table below (we also provide calculations assuming 5% dropout after the first week). Power was calculated based on simple logistic regression with a binary predictor assuming an alpha level of 0.05 ([Hsieh et al, 1998](#)).

Table 13.7.1.1 Power justification of the Primary Objective in adults and children

Population	Comparison	Comparison group sample size	Reference group sample size	Minimum detectable odds ratio at 80% power	
				Assuming target sample size	Assuming 5% dropout
Adults	AD vs. Non-AD	260	100	1.95	1.99
	Moderate-to-severe AD vs. Mild AD	160	100	2.06	2.10
Children	AD vs. Non-AD	130	50	2.60	2.68
	Moderate-to-severe AD vs. Mild AD	80	50	2.80	2.89

Additionally, Figure 13.7.1.1 displays a range of power scenarios for these comparisons of interest.

Figure 13.7.1.1 Power curves for association tests in the Primary Objective

Note that the primary objective includes Day 7 data only, and therefore will not be impacted by participant dropout during the study.

Power analysis for Secondary Objective #1

SO1 is as follows: to determine how gene expression in the skin (skin tape) differs between non-AD participants and those with current mild or moderate-to-severe AD disease.

[figure not shown]
Assuming a gene expression coefficient of variation (CV) of 0.4 to approximate the observed median CV value across genes in humans ([Hart et al, 2013](#)), as well as the group-level sample sizes in Table 13.7.1.2, we have 80% power to detect statistical significance for the fold changes listed in Table 13.7.1.2. Power was calculated using the RNA-seq power computation method of [Hart et al, 2013](#). The significance threshold (α) was set at 0.05/10,000, assuming ~10,000 expressed genes with sufficient variability to test. Finally, we assumed the least powerful situation for identifying differential expression, which is for genes that are lowly expressed (10 reads per gene). We calculated power assuming both our target sample sizes as well as for the case of 20% dropout by end of study.

Table 13.7.1.2 Power justification of Secondary Objective #1 in adults and children

				Minimum detectable fold change at 80% power	
Population	Comparison	Comparison group sample size	Reference group sample size	Assuming target sample size	Assuming 20% dropout
Adults	AD vs. non-AD	260	100	1.38	1.44
	Mild AD vs. non-AD	100	100	1.48	1.55
	Moderate-to-severe AD vs. non-AD	160	100	1.42	1.48
	Moderate-to-severe AD vs. Mild AD	160	100	1.42	1.48
Children	AD vs. non-AD	130	50	1.58	1.67
	Mild AD vs. non-AD	50	50	1.74	1.85
	Moderate-to-severe AD vs. non-AD	80	50	1.64	1.74
	Moderate-to-severe AD vs. Mild AD	80	50	1.64	1.74

Additionally, Figure 13.7.1.2 displays a range of power scenarios for these comparisons of interest.

Figure 13.7.1.2 Power curves for differential expression analyses in SO1. A) Assuming target sample sizes. B) Assuming sample sizes after 20% dropout by end of study.

Note that SO1 will assess differences in gene expression at both Day 7 and End of Study (Day 168-224).

Power analysis for Secondary Objective #2

SO2 is as follows: to determine how gene expression in the skin (skin tape) changes over time among the study outcome groups: (1) topical steroid responders, (2) dupilumab responders, (3) dupilumab non-responders, (4) non-AD, and (5) long-term dupilumab participants.

[figure not shown]
Anticipated group sample sizes are based on the targeted population sample sizes and assumed treatment response rates described in [Section 13.7.1](#). The method for power calculation and underlying assumptions (gene expression CV, alpha, etc.) were identical to those used for SO1. Based on these assumptions, we have 80% power to detect statistically significant fold changes in gene expression between the study start and end points for the groups and fold changes listed in Table 13.7.1.3. Again, we calculated power for both our target samples sizes as well as for the case of 20% dropout by end of study.

Table 13.7.1.3 Power justification for Secondary Objective #2 in adults and children

Population	Study outcome group	Sample size	Minimum detectable fold change at 80% power	
			Assuming target sample size	Assuming 20% dropout
Adults	Topical steroid responders	175	1.34	1.39
	Dupilumab responders	34	1.95	2.11
	Dupilumab non-responders	51	1.73	1.84
	Non-AD	100	1.48	1.55
	Long-term dupilumab	40	1.85	1.99
Children	Topical steroid responders	87	1.52	1.60
	Dupilumab responders	17	2.57	2.88
	Dupilumab non-responders	26	2.15	2.35
	Non-AD	50	1.74	1.85
	Long-term dupilumab	20	2.39	2.65

Additionally, Figure 13.7.1.3 displays a range of power scenarios for these expression changes of interest.

Figure 13.7.1.3 Power curves for differential expression analyses in SO2. A) Assuming target sample sizes. B) Assuming sample sizes after 20% dropout by end of study.

Note that SO2 will assess differences in gene expression between Day 7 and End of Study (Day 168-224).

14 Identification and Access to Source Data

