Clinical heterogeneity in response to therapy is also consistent with AD being a complex, multi-factorial disease, caused by the interaction of a large number of genetic and environmental risk factors. Selection of new mechanistically directed medications, like the type 2-inhibitor, dupilumab, based on carried endotype, would greatly benefit patients. For example, the type 2-high AD endotype, which exhibits more severe disease ([Dyjack et al, 2018](#)), likely represents a patient subgroup who would be responsive to such emerging type 2 inhibitor therapies ([Guttman-Yassky et al, 2019](#)). In support of this, dupilumab therapy has been shown to only clear or nearly clear approximately 40% of subjects ([Beck et al, 2014](#)), nearly matching the AD type 2-high frequency observed in our study. Other endotypes, yet to be discovered, may be poorly served by any existing therapies.

The overall premise of this study is that clinical management of AD patients will require person-level delineation of the multiple endotypes driving disease in this group. Elucidation of these endotypes will occur by way of a well-controlled examination of skin function at the whole transcriptome sequence (WTS) level, allowing for the sampling of possible epidermal, immune, and mesenchymal components of AD skin. Advanced technologies like single cell Ribonucleic Acid sequencing (scRNA-seq) will enable a comprehensive determination of the cell types and functions that are altered to drive particular disease endotypes. We posit that many of these endotypes will modify the lipid and protein components of the epidermis, which then go on to alter skin phenotype and function. Lastly, a combination of genetic risk and non-atopic clinical features such as skin microbial dysbiosis may underlie AD endotypes and/or disease severity. Our ultimate goal through these examinations will be to develop evidence-based, precision medicine approaches to address disease in the most burdened AD patients. Ultimately, knowledge from this study will facilitate development of biomarkers and discovery of pathways to target for the treatment of AD subjects who are not responsive to currently available topical and systemic therapies.

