Dupilumab is a fully human mAb directed at interleukin-4 receptor alpha (IL-4R α), thus interfering with signaling by both IL-4 and IL-13, two key type 2 cytokines ([Hamilton et al, 2015](#)). Treatment of AD patients with dupilumab was shown to suppress molecular markers of cutaneous and systemic type 2 inflammation, as well as reverse epidermal abnormalities that coincided with clinical improvement ([Guttman-Yassky et al, 2019](#)). In two phase 3 trials, adult patients with moderate-to-severe AD inadequately controlled on topical treatment were treated with dupilumab, 600 mg loading dose followed by 300 mg weekly or Q2W, or placebo by subcutaneous injection ([Simpson et al, 2016](#)). The primary outcome of an Investigator Global Assessment (IGA) of 0 or 1 (clear or almost clear) and a reduction of 2 points or more in that score from baseline at week 16 was achieved by 36-38% of patients on dupilumab monotherapy at week 16 versus 8-10% on placebo ($p<0.001$). In addition, improvement of at least 75% in Eczema Area and Severity Index (EASI-75) from baseline to week 16 was reported in ~50% of patients on dupilumab. A number of other clinically relevant outcome measures including pruritus scores and patient reported outcome measures were also significantly improved in the patients treated with the biologic. Injection-site reactions and conjunctivitis were more frequent in the dupilumab treated patients than in the placebo groups. The conjunctivitis was for the most part self-limited, and only 1 patient in the phase 3 monotherapy trials discontinued study treatment. A recent review of randomized placebo-controlled trials of dupilumab in AD, asthma, chronic rhinosinusitis with nasal polyps (CRSwNP) and eosinophilic esophagitis (EoE) found that the incidence of conjunctivitis was more frequent with dupilumab treatment in most AD trials but very low and similar to that seen in placebo treated patients in the asthma, CRSwNP and EoE trials ([Akinlade et al, 2019](#)). Greater baseline AD disease severity and history of prior conjunctivitis were associated with increased conjunctivitis incidence. Of note, conjunctivitis was mostly mild-to-moderate in severity, and most cases recovered or resolved while continuing on dupilumab. Data from a blinded, placebo-controlled trial demonstrated that patients treated with dupilumab had

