decreased *S. aureus* colonization and increased microbial diversity that correlated with clinical improvement of AD and biomarkers of type 2 immunity ([Callewaert et al, 2020](#)).

In a randomized, double-blind, parallel-group, phase 3 monotherapy trial in 251 adolescent patients ages 12-17 years with moderate-to-severe AD, patients were stratified to 16-weeks of treatment with 1 of 4 regimens: dupilumab 400 mg loading dose, then 200 mg Q2W (baseline weight <60 kg); dupilumab 600 mg loading dose, then 300 mg (baseline weight ≥60 kg) Q2W; dupilumab 600 mg loading dose, then 300 mg Q4W; or placebo with all patients receiving injections Q2W to maintain study blinding ([Simpson et al, 2020](#)). A significantly higher proportion of patients treated with dupilumab achieved EASI-75 and IGA 0 or 1 at week 16 vs placebo treated patients. Efficacy of the Q2W regimen was generally superior to the Q4W regimen. The incidence of conjunctivitis in the dupilumab treated patients (~10%) was similar to that seen in the adult trials. Most recently, dupilumab together with TCS was studied in children 6-11 years with severe AD; 367 patients were randomized 1:1:1 to dupilumab 300 mg Q4W, weight based dupilumab (100 mg Q2W, baseline weight <30 kg; 200 mg Q2W, baseline weight ≥30 kg), or placebo with concomitant medium-potency TCS in a double-blind 16 week phase 3 trial ([Paller et al, 2020](#)). Both the Q4W and Q2W dupilumab + TCS regimens resulted in clinically meaningful and statistically significant improvement in signs, symptoms, and quality of life (QOL) versus placebo + TCS in all pre-specified endpoints. For Q4W, Q2W, and placebo, 32.8%, 29.5%, and 11.4% of patients, respectively, achieved IGA scores of 0 or 1; 69.7%, 67.2%, and 26.8% achieved ≥75% improvement in EASI scores; and 50.8%, 58.3%, and 12.3% achieved ≥4-point reduction in worst itch score. Conjunctivitis and injection-site reactions were more common with dupilumab + TCS than with placebo + TCS. Dupilumab is approved in the United States (US) for patients age ≥ 6 months with moderate-to-severe AD uncontrolled by topical prescription medicines or when those medications are not advised. The reason patients with AD do not consistently respond to dupilumab is unknown.

2 Study Objectives, Endpoints, and Hypotheses

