4.1 Rationale for Study Population

This study will enroll male and female, adult and pediatric participants, 6 years of age and older. Participants with mild (EASI ≤ 7) and moderate-to-severe (EASI > 7) AD will be enrolled as our objective is to study all severities of AD and their response to all steps in AD management per protocol standard-of-care. NAD participants will be needed as a control population to compare to AD. As AD is often transient at younger ages and we are trying to study more stable endotypes/phenotypes, enrollment will be limited to those 6 years of age and older. Both sexes and all racial groups will

be included to study the full spectrum of clinical AD. We will monitor the enrollment distribution by age, sex, and race/ethnicity in the three enrollment groups (NAD, DNAD, LTD). Any detected skews accruing during enrollment will be addressed by instructing sites to target unrepresented groups.

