10. DNAD and LTD participants must have a history of chronic AD, (according to the Atopic Dermatitis Research Network [ADRN] Standard Diagnostic Criteria [[Appendix B](#)]), that has been present for at least 1 year before the Screening Visit.
11. DNAD and LTD participants must agree to refrain from applying topical steroid to a specified target area between the Baseline Assessment and Day 7 Visits.

DNAD Participants:

12. DNAD participants must have active lesions on the upper or lower extremities or trunk of sufficient size and in the required locations, as specified in the study manual of procedures (MOP), for specimen collection at the Baseline Assessment and Steroid Initiation (Day 7) Visits.

LTD Participants:

13. LTD participants must be currently receiving dupilumab and must have started dupilumab treatment ≥ 4 months prior to the Screening Visit.

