6.2 Disposition of Subjects

Study participants, whether child or adult, will be allocated to the following diagnostic groups prior to analysis:

- I. *Non-AD*
Participants never diagnosed with AD.
- II. *Dupilumab-naïve AD participants*
AD participants never taking dupilumab.

There are two possible AD severity groups:

1. Mild AD (EASI ≤ 7 at analysis timepoint)
2. Moderate-to-severe AD (EASI > 7 at analysis timepoint)

There are three possible outcome groups:

1. Topical steroid responders: Those on topical steroid who never obtain an EASI score > 7 by the 12-Week Steroid Assessment visit (EASI score > 7 obtained after that point will lead to early study termination).
2. Dupilumab responders: Steroid non-responders on dupilumab who obtain an EASI score ≤ 7 at the 15-Week Dupilumab Assessment visit (regardless of EASI scores obtained before or after that visit).
3. Dupilumab non-responders: Those on dupilumab who fail to obtain an EASI score ≤ 7 at the 15-Week Dupilumab Assessment visit (regardless of EASI scores obtained before or after that visit).

- III. *Long-term dupilumab AD participants*
AD participants already on dupilumab (for ≥ 4 months) at the start of the study. These patients will continue dupilumab treatment as prescribed by their physician outside of the study.

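### The 40% dupilumab response rate behind Table 13.7.1.3 is the rate the protocol elsewhere gives for clear or nearly clear skin, so the responder/non-responder split at EASI ≤ 7 is unsupported and probably has too many non-responders

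*Protocol*

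**What the plan says.** Protocol 13.7.1 projects topical steroid failure ("we project a 50% failure rate for topical steroids among the dupilumab-naïve moderate-to-severe participants and a 5% failure" rate for mild participants) and so expects 85 adults and 43 children to start dupilumab. Of those treated, "during the study, we expect that approximately 40% will achieve" EASI ≤ 7, with one dupilumab trial in adults cited as support. Table 13.7.1.3 then lists 34 responders and 51 non-responders among adults, and 17 and 26 among children.

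Protocol 1.1 cites the same trial for a different outcome: "dupilumab therapy has been shown to only clear or nearly clear approximately 40% of subjects".

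SAP 6.2 defines dupilumab responders as "Steroid non-responders on dupilumab who obtain an EASI score ≤ 7 at the 15-Week Dupilumab Assessment visit". What EASI ≤ 7 means in this study is given in Protocol 4.1: "Participants with mild (EASI ≤ 7) and moderate-to-severe (EASI > 7) AD will be enrolled". A dupilumab-naïve participant at that level still has visible disease, because Protocol 4.2 requires that "DNAD participants must have active lesions on the upper or lower extremities or trunk of sufficient size".

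**The concern.** One number from one source is attached to two endpoints that are not equivalent here. A participant can satisfy EASI ≤ 7 and still carry active lesions, so a rate for clear or nearly clear skin should sit below the rate for EASI ≤ 7. Neither document gives any other support for 40% at EASI ≤ 7, and the SAP does not revisit it.

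Protocol 1.3 shows how far the rate can move when the criterion is eased. In the adult monotherapy trials, IGA 0 or 1 was reached by 36–38%, while EASI-75 "was reported in ~50% of patients on dupilumab". In the trial of children aged 6–11 years with severe disease on concomitant topical steroid, IGA 0 or 1 was reached by 32.8% and 29.5% on the two dupilumab regimens. For those regimens and placebo in turn, "69.7%, 67.2%, and 26.8% achieved ≥75% improvement in EASI scores". Two features of this study also point upward. Dupilumab can start at any EASI above 7, so some participants need little improvement to cross the line, and topical steroid is allowed on non-target lesions (Protocol 3.1.1).

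At stake are the sizes of two of the five SO2 outcome groups and the detectable fold changes printed for them.

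**Working it through.** **Inputs.** From Protocol 13.7.1: steroid failure 50% (moderate-to-severe) and 5% (mild); targets of 160 and 100 adults, and 80 and 50 children; dupilumab response 40%; CV 0.4; 10 reads per gene; α = 0.05/10,000 = 5 × 10⁻⁶; power 80%; 20% dropout scenario. The protocol does not state the sidedness of α. Two-sided reproduces the table; one-sided does not (1.70 instead of 1.73 at n = 51).

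**Group sizes as planned.**
- Adults: 0.50 × 160 + 0.05 × 100 = 85 starters; 0.40 × 85 = 34 responders; 0.60 × 85 = 51 non-responders.
- Children: 0.50 × 80 + 0.05 × 50 = 42.5, rounded to 43; 0.40 × 43 = 17.2, shown as 17; 0.60 × 43 = 25.8, shown as 26.

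**Detectable fold change as planned.** FC = exp[(z₁₋α/₂ + z₀.₈₀) × √(2 × (1/depth + CV²)/n)]. The two z values sum to 4.565 + 0.842 = 5.406, and 1/10 + 0.4² = 0.26, so FC = exp[5.406 × √(0.52/n)].
- n = 51 gives 1.726 and n = 26 gives 2.148 (stated 1.73 and 2.15).
- n = 34 gives 1.952 and n = 17 gives 2.574 (stated 1.95 and 2.57).
- With 0.8n, the non-responder rows give 1.841 and 2.351 (stated 1.84 and 2.35).

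All ten rows of Table 13.7.1.3 match to two decimals in both columns. The arithmetic is right; the question is the 40% input.

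**Varying the response rate.** The rates above 40% are assumptions. Each cell gives n, then the fold change at target size. At 50% the half-participants are kept; at 70% the adult split of 59.5/25.5 is shown as 59/26.

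| Response | Adult responders | Adult non-responders | Child responders | Child non-responders |
|---|---|---|---|---|
| 40% (plan) | 34; 1.95 | 51; 1.73 | 17; 2.57 | 26; 2.15 |
| 50% | 42.5; 1.82 | 42.5; 1.82 | 21.5; 2.32 | 21.5; 2.32 |
| 60% | 51; 1.73 | 34; 1.95 | 26; 2.15 | 17; 2.57 |
| 70% | 59; 1.66 | 26; 2.15 | 30; 2.04 | 13; 2.95 |

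With 20% dropout, the non-responder fold changes at 50%, 60% and 70% are 1.95, 2.11 and 2.35 in adults (stated 1.84), and 2.56, 2.88 and 3.35 in children (stated 2.35).

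Read the other way, power to detect the stated 1.73 in adult non-responders falls from 80% to about 65%, 45% and 25%. Power to detect the stated 2.15 in child non-responders falls to about 64%, 43% and 23%.

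**Responder versus non-responder contrast.** With a common variance, its standard error is proportional to √(1/n₁ + 1/n₂). For adults this is 0.221 at 40%, 0.217 at 50%, 0.221 at 60% and 0.235 at 70% (0.237 with the unrounded 59.5/25.5). The loss at 70% is therefore 6–7%. The unrounded children's groups show the same ratios.

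**The case against.** The case on the other side has several parts, and much of it stands.

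- **The documents do not fix the true rate.** The cited trial may report both endpoints, or section 1.1 may be the loose paraphrase. A reader might infer that the non-responder group is overstated by a known amount. The documents do not support that; they support a direction, conditional on 40% being the clear/nearly-clear rate.
- **The 50–70% range borrows from another endpoint.** EASI-75 is a relative change. It guarantees EASI ≤ 7 only from a start of 28 or less (28 × 0.25 = 7), and no distribution of EASI at dupilumab start is given. The 67–70% figures come from children aged 6–11 with severe disease on topical steroid; the only adult EASI-75 figure is about 50%. Dupilumab starters here have also just failed topical steroid, which could pull the rate down. The upper end is therefore least secure for adults.
- **The effect runs both ways.** The weakest dupilumab rows are already the responders. At 60% the two groups simply exchange sizes, so the worst printed fold change gets worse only above 60%. It would be wrong to infer that the dupilumab analyses as a whole lose power.
- **SO1 is not shown to be affected.** A reader might carry the point into Table 13.7.1.2 through the End of Study severity groups. That table does not use the 40% and has no separate End of Study rows. SAP 6.2 also fixes response at the 15-week visit whatever the later EASI, so non-response is not the same as moderate-to-severe disease at End of Study.
- **The stated fold changes are conservative in other respects.** They use 0.05/10,000 and a gene with 10 reads, whereas SAP 9.2.1 controls the false discovery rate at 5%. This is true, but it does not supply a basis for the 40%.

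Nor do the documents rank non-responders above the other SO2 groups. What remains is the mismatch itself and the two pairs of table rows computed from it.

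**Conclusion.** The input is wrong as written: the same citation and the same 40% support two different endpoints, and the rows of Table 13.7.1.3 rest on the one for which no separate support is given. If 40% is the clear/nearly-clear rate, 51 and 26 are upper limits for non-responders and 34 and 17 are lower limits for responders. This assumes that participants who are clear or nearly clear would also have EASI ≤ 7. The size is not established; the 50–70% range is illustrative. Even its mildest step, 50%, takes power at the stated non-responder fold changes from 80% to about 65%. The responder rows gain, and the contrast between the two groups is nearly unchanged up to 60%. The primary objective, which drives the sample size, is unaffected.

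**What to change.** - Reconcile Protocol 1.1 and 13.7.1: say which endpoint the cited 40% belongs to.
- Give a source for the week-15 EASI ≤ 7 rate, separately for adults and children. If there is none, replace the single 40% with a range, for example 40%, 50%, 60% and 70%.
- Restate both the responder and the non-responder rows of Table 13.7.1.3 over that range, at target size and with 20% dropout, so that the gain in one group and the loss in the other are both visible.

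No change to Table 13.7.1.2, the primary objective or enrolment is needed. The cost is protocol text and one table; some non-responder figures will look less favourable and some responder figures more so.
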